1.3.1 Study #1: Mapping disorder-specific brain activation in patients with SD vs. SD/VT using fMRI during symptomatic voice and speech production. We will use a sparse-sampling event-related BOLD fMRI design on a 3.0 Tesla Philips MRI scanner. We already successfully used this design for the investigations of voice and other laryngeal behaviors (Loucks et al., 2007; [name] et al., 2007; [name] et al., 2009; [name] and Ludlow, 2010). Brain activity will be studied during production of 10 symptomatic speech sentences (e.g., "We eat eels every day", "Sam has a rabbit in his hand") and syllables (repetitive vowel /i/ and continuous vowel /i/). In the scanner, subjects will listen to an auditory example of the task presented in a pseudorandomized order and reproduce it within the 5-s interval of the 'silent' period of scanning, only after which a 2-s image acquisition will follow, while the subjects remain silent and motionless. A resting condition without auditory presentation will serve as a baseline. Four scanning sessions will be acquired with a total of 36 experimental trials and 24 baseline conditions. Structural MRI will be acquired for an anatomical reference.

Data analysis will follow the similar processing pipeline as previously employed by us using AFNI software ([name] et al., 2007; [name] et al., 2009; [name] and Ludlow, 2010). Following initial data processing, the task-related responses will be analyzed using multiple linear regression with a single regressor for each task convolved with a canonical hemodynamic response function. Baseline drifts will be modeled using quadratic polynomials in time for each separate imaging run, and motion parameter estimates will be used as additional regressors of no interest in the multiple regression analysis. To account for disorder-specific vocal motor differences between SD and SD/VT groups, such as adductor and abductor voice breaks and shakiness, respectively, we will include the number of voice breaks and severity of voice tremor as variables in a within-group statistical analysis. Quantitative measures of SD and VT symptoms will be derived from the *Study 1.3.3* within this Aim. The correction of individual statistical parametric maps for multiple comparisons will be performed using Monte-Carlo simulations (Forman et al., 1995), which will identify a minimum cluster size at a voxelwise threshold of 0.005 at overall significance level of a corrected $p \leq 0.025$.

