Data analysis. Similar to our recent study in SD ([name] and Ludlow, 2011), brain volume in each subject will be segmented into gray matter, white matter, and CSF. VBM analysis will follow the standard procedure using VBM8 toolbox in the SPM8 software. Spatial normalization will be performed using a diffeomorphic nonlinear registration tool (DARTEL) to improve inter-subject registration (Ashburner, 2007). Voxelwise statistical differences in GMV between groups will be examined using independent t -tests with age, gender, total intracranial volume, number of SD-specific voice breaks, severity of tremor and disorder duration as nuisance effects (Ashburner and Friston, 2000). The cluster-level significance will be assessed using a conservative non-stationary cluster extent correction (Hayasaka and Nichols, 2004) at $p \leq 0.025$.

Study population and Sample size. The same 3 groups of SD, SD/VT and healthy control subjects recruited for the fMRI study will participate in this study. To determine the sample size for this study, we reviewed our previous study in 40 SD patients and 40 controls ([name] and Ludlow, 2011). That study found increased GMV in the laryngeal primary sensorimotor cortex (HV vs. SD: 0.22 ± 0.04 vs. 0.26 ± 0.04). Using these values, t -test indicated that a sample size of 17 subjects per group will provide 80% power to detect group differ-

ences at a 0.025 significance level in the present study. To increase statistical power of the proposed studies and account for subjects' dropout possibilities, we will recruit the same 20 subjects per group, who participate in the 1.3.1. *Study #1*.

1.3.3 Study #3: Mapping disorder-specific white matter abnormalities in patients with SD vs. SD/VT using DTI.

In this study, we propose to identify white matter abnormalities contributing to SD and SD/VT using DTI on a 3.0 Tesla Philips scanner. Whole-brain brain images will be acquired using spin-echo EPI sequence with paired gradient pulses for diffusion weighting; diffusion will be measured along at least 33 non-collinear directions. We successfully used a similar scanning protocol in our previous studies ([name] et al., 2008; [name] et al., 2009).

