Study population and Sample size. To estimate the number of subjects in this study, we reviewed our recent DTI studies, which used a similar experimental design to examine white matter abnormalities in SD patients and controls ([name] et al., 2008; [name] et al., 2009). Significantly decreased FA was found in the right genu of the internal capsule in SD (patients vs. controls: 0.55 ± 0.05 vs. 0.61 ± 0.07). Using these values, a power of 80% at a 0.025 significance level will be obtained with 18 subjects per group for the proposed study based. Again, to increase the statistical significance and allow for between-study comparisons, we propose to recruit the same 20 subjects per SD, SD/VT and control group for the DTI study. The statistical power for tractography is the same.

1.3.4 Study #4: Relationship between brain abnormalities and clinico-behavioral characteristics in SD and SD/VT.

The role of neuroimaging studies in elucidation of pathophysiological mechanisms of SD would be considerably enhanced if coupled with strategies that yield information about their relevance to symptom elicitation. Additionally, identification of disorder-specific brain abnormalities that are correlated with disorder symptoms can prove useful for assessment of efficacy of existing and newly developed therapeutic interventions. Our approach here will be to examine the relationships of functional brain activity and structural brain organization with clinico-behavioral correlates (i.e., disorder severity scores). For all 20 subjects per group (both patients and controls), the behavioral measures will be obtained during initial intake screening, history and physical examination, and three-tiered diagnostic questionnaire (see *Appendices 1 and 2*). Patients' voice and speech will be digitally recorded during scanning for offline acoustic analysis to assess the SD and VT severity.

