Data analysis. Blinded analysis of patients' voice samples will be performed to quantify the disorder severity, including the frequency of SD-specific voice breaks, voice harshness, breathiness, and voice tremor (see *Appendix 2*). In each patient group, unbiased whole-brain voxelwise Pearson's correlation coefficients will be computed to determine the relationships among brain activation (measured as percent BOLD signal change) and symptom severity at a corrected $p \leq 0.025$ using AFNI software ([name] and Ludlow, 2011). Similarly, whole-brain voxelwise Pearson's correlation coefficients will be used to assess relationships among measures of structural abnormalities (i.e., derived from VBM and DTI analyses) and quantitative measures of SD and VT symptoms (i.e., number of voice breaks, voice harshness, breathiness and voice tremor derived from voice and speech acoustic analysis). The alpha level will be set at $p \leq 0.025$ to correct for multiple comparisons.

1.4 Expected Outcomes. Upon the successful completion of the proposed studies in Specific Aim #1, it is our expectation that each disorder will have been found to exhibit a unique pattern of functional and structural al-

terations within the cortico-basal ganglia-thalamo-cortical and cerebello-thalamo-cortical networks. These findings will significantly advance our knowledge of SD and VT pathophysiology by establishing the concept that functional brain abnormalities in SD follow distinctive patterns when combined with VT. We expect that these findings will be fundamental in defining the neuroimaging markers of these disorders, which can be used for prediction and better differential diagnosis of SD and VT.

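### Study 1.3.4 correlates brain measures with symptoms in each patient group without stated adjustment for age, gender or head size, and has no test that could show a link to be specific to one disorder

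*Combined protocol and SAP*

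**What the plan says.** Under 1.3.4 Study #4, Data analysis, the method for activation is: "In each patient group, unbiased whole-brain voxelwise" Pearson coefficients, relating percent BOLD change to symptom severity. The next sentence applies the same method to the VBM and DTI measures, against "number of voice breaks, voice harshness, breathiness and voice tremor derived from voice and speech acoustic analysis". The error control is given as "The alpha level will be set at $p \leq 0.025$ to correct for multiple comparisons". No covariate is named, and no comparison of the correlations between SD and SD/VT is described.

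The opening of 1.3.4 gives part of the motivation: "identification of disorder-specific brain abnormalities that are correlated with disorder symptoms can prove useful for assessment of efficacy". Section 1.4 expects each disorder to show its own pattern of functional and structural alterations.

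Four other places bear on this:
- 1.3.2 Study #2, Data analysis, runs the GMV group comparisons "with age, gender, total intracranial volume, number of SD-specific voice breaks, severity of tremor and disorder duration as nuisance effects".
- 1.3 Research Design matches SD and SD/VT patients on age, gender, SD type and reported alcohol effect.
- The inclusion criteria allow ages 21 to 80.
- Between-group comparisons are planned for activation, connectivity, GMV and FA/MD (1.3.1 to 1.3.3), but not for the brain-symptom relation.

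**The concern.** There are two separate issues.

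The first is confounding within a group. If a symptom worsens with age and a brain measure changes with age, the two will correlate even when neither has anything to do with the other. Matching the groups on age does not help, because a within-group correlation depends on the age spread inside the group. The plan already regards age, gender and head size as nuisance for GMV when groups are compared, but does not say so when the same measure is correlated with symptoms.

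The second is what the output can support. The only product specified is one correlation map per group. A cluster that is significant in SD/VT and absent in SD is easily read as a disorder-specific link, but two separate tests do not test a difference. The group contrasts in Studies 1.3.1 to 1.3.3 show differences in level, not in how level relates to symptoms. The results are meant to feed neuroimaging markers and differential diagnosis, so both issues bear on what is claimed.

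**Working it through.** Study 1.3.4 states no power, effect size or error rate of its own, so there is no plan figure to reproduce.

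**Inputs.** From the plan: 20 patients per group; alpha 0.025 (sidedness not stated for the correlations, taken as two-sided); and, as a sensitivity value, the 1.3.1 rule of "a minimum cluster size at a voxelwise threshold of 0.005". Assumed, because the documents give no figures: age-brain and age-symptom correlations, and the true brain-symptom correlation. All rates are for a single voxel or region.

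**1. Critical correlation.** r_crit = t / √(df + t²), with df = 18. At 0.025, t = 2.445, so r_crit = 2.445/√(18 + 5.978) = 0.499. At 0.005, r_crit = 0.602.

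**2. Age alone, no direct brain-symptom link.** The induced correlation is the product of the two age correlations. A negative age-brain correlation changes its sign but not the two-sided rate. Simulated at n = 20, two-sided 0.025:

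| Age-brain / age-symptom (size) | Induced r | False positives, unadjusted | Adjusted for age |
|---|---|---|---|
| 0.3 / 0.3 | 0.09 | 3.5% | 2.5% |
| 0.5 / 0.4 | 0.20 | 8% | 2.5% |
| 0.5 / 0.5 | 0.25 | 11.8% | 2.5% |
| 0.6 / 0.5 | 0.30 | 17% | 2.5% |

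The adjusted test is the partial correlation (r_xy − r_xa·r_ya) / √[(1 − r_xa²)(1 − r_ya²)] on 17 df, with critical value 0.512.

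**3. Same true correlation in both disorders.** With per-group power p, the chance that exactly one group is significant is 2p(1 − p). This cannot exceed 50%.

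| True r in both | p at 0.025 | Exactly one significant |
|---|---|---|
| 0.3 | 0.168 | 28% |
| 0.4 | 0.318 | 43% |
| 0.5 | 0.523 | 50% |
| 0.6 | 0.750 | 38% |
| 0.7 | 0.922 | 14% |

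At a 0.005 threshold the figures are 11% (r = 0.3), 41% (0.5) and 50% (0.6).

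**4. An example.** Observed r = 0.55 in one group is significant and 0.30 in the other is not. Fisher z difference: 0.618 − 0.310 = 0.309 before rounding. SE = √(1/17 + 1/17) = 0.343. Ratio 0.90, p = 0.37. The data do not separate the two correlations.

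**5. What a direct test can do.** With equal slopes (r = 0.5 in both groups), the group-by-symptom interaction is significant in about 2.5% of simulated trials, the nominal level. Its power is limited. Using the Fisher z comparison as a guide, significance needs a z difference above 2.241 × 0.343 = 0.769. For 80% power, (2.241 + 0.842) × 0.343 = 1.057, which is r = 0.78 against 0. Power is 41% for 0.6 versus 0 and 21% for 0.6 versus 0.2.

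**The case against.** A reader might infer that the plan declares a link disorder-specific whenever it is significant in one group only. The documents do not say that. In 1.3.4 the term qualifies brain abnormalities, and the expected pattern in 1.4 is one of alterations, not of correlations. Those alterations have group comparisons of their own. If Study 1.3.4 asks only whether a measure tracks symptoms within each disorder, a within-group correlation is a suitable design. This stands. The point is therefore limited to what the output can support, not to a rule the plan has adopted.

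A reader might also infer that age would create disorder-specific links. With age-matched groups, a common age effect tends to induce the same spurious correlation in both. A one-group result would need chance or a different age-symptom relation in each group.

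The age figures are assumptions. At 0.3/0.3 the inflation is small, and 21 to 80 is an eligibility window. Onset is usually between 40 and 55, and the age spread that will be recruited is unknown.

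Silence on covariates is not a decision against them. Measures derived from VBM might be meant to carry the VBM nuisance terms. The text does not say so, and that set could not be carried over whole, because it includes voice breaks and tremor severity, two of the symptoms to be correlated. No covariates are named for DTI.

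Finally, whole-brain correction will change the absolute rates. It does not turn two separate tests into a test of difference.

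**Conclusion.** The concern holds in two limited forms. First, the correlations have no stated adjustment for age, gender or, for GMV, intracranial volume. Under the assumed age correlations this raises the single-voxel false-positive rate from 2.5% to between 3.5% and 17%, with the spurious link probably appearing in both groups. Second, the plan contains no test that could support a claim that a brain-symptom link differs between SD and SD/VT. If such a claim were made from the separate maps, an identical link would be significant in exactly one group about 14% to 50% of the time for true correlations of 0.3 to 0.7. The 50% is the mathematical ceiling, reached near r = 0.5, and is not a forecast of how often a false claim would be published. The calculations assume normal data, two-sided testing at 0.025 and 20 analysable patients per group.

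**What to change.** Change the Data analysis text of 1.3.4 as follows.

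- Replace the plain Pearson coefficients with partial correlations, or an equivalent GLM, adjusted for age and gender, plus total intracranial volume for GMV. State that the symptom scores listed as nuisance in 1.3.2 are not carried over. Say whether disorder duration is included; a sensitivity analysis would do.
- For symptoms present in both groups (breaks, harshness, breathiness), fit one model across the 40 patients: brain measure on group, symptom, group × symptom, age and gender, plus intracranial volume for GMV. Call a link disorder-specific only on the interaction.
- Analyse tremor within SD/VT only, adjusted in the same way.
- Report the per-group maps as descriptive.

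The variables are already planned: group and symptom scores in 1.3.4, the covariates in 1.3.2. The cost is degrees of freedom: within a group, 18 falls to 16 with age and gender, or 15 with intracranial volume; the pooled model leaves 40 − 6 = 34, or 33. The larger cost is candour about power. At 20 versus 20 the interaction will miss most real differences short of about r = 0.78 against 0, so a non-significant interaction must not be read as showing that a link is shared, and few specificity claims will be supportable.

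### Study 1.3.4 presents an alpha of 0.025 as its multiple-comparison correction, but nothing adjusts across the roughly 28 to 32 brain-symptom maps that its measures imply

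*Combined protocol and SAP*

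**What the plan says.** The data analysis paragraph of Study 1.3.4 describes two sets of correlations.

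- **Functional.** "In each patient group, unbiased whole-brain voxelwise Pearson's correlation coefficients will be computed", relating percent BOLD signal change to "symptom severity at a corrected $p \leq 0.025$ using AFNI software".
- **Structural.** Introduced as similar to the first set, this relates VBM and DTI measures to the "number of voice breaks, voice harshness, breathiness and voice tremor derived from voice and speech acoustic analysis". It closes with: "The alpha level will be set at $p \leq 0.025$ to correct for multiple comparisons".

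Neither the sentence beginning "The alpha level will be set at" nor the rest of the paragraph gives a number of tests, a family or a primary correlation. For the structural maps it names no voxel-level method.

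Other sections use the same 0.025 as a level within one analysis map:

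- Study 1.3.1 reaches it from a voxel threshold of 0.005 plus a Monte Carlo minimum cluster size, and does so again for the connectivity maps.
- Study 1.3.2 applies a non-stationary cluster-extent correction at 0.025 to the GMV group comparisons.
- Study 1.3.3 uses an adjusted 0.025 over the white matter skeleton for FA and MD.

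On purpose, the introduction to Study 1.3.4 says that "identification of disorder-specific brain abnormalities that are correlated with disorder symptoms can prove useful for assessment of efficacy" of treatments.

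**The concern.** A threshold of 0.025 does not correct for a family of maps unless it was derived from the size of that family. Here the family is undefined and, on the measures listed, large. A correction over voxels deals with the many locations inside one map. It does nothing about repeating the exercise for several symptoms, several imaging measures and two groups.

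What is at stake is false assurance. With 20 patients per group, a chance brain-symptom correlation could be reported as already corrected for multiplicity and then taken up when treatments are assessed. A reader would have no reason to discount it.

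**Working it through.** **The plan's figure.** The plan gives no derivation of 0.025 and no family-wise rate, so there is nothing to reproduce.

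**Counting the maps.**

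- Patient groups analysed separately: 2 (Study 1.3.4).
- Symptom measures: 4 (Study 1.3.4).
- Imaging measures: 4, namely BOLD (Study 1.3.4), GMV (Study 1.3.2), and FA and MD (Study 1.3.3).
- Total: 2 × 4 × 4 = 32.
- Without tremor maps in the SD group, which has no VT: 32 − 4 = 28.

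**Reading A: 0.025 is the whole-brain corrected level of each map.** With k maps and no true association, the expected number of false maps is 0.025k, whatever the dependence. For independent maps the family-wise error is 1 − 0.975^k.

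| Reading of the text | k | Family-wise error if independent |
|---|---|---|
| One BOLD severity score, no SD tremor maps: (1 + 3×3) + (1 + 4×3) | 23 | 44% |
| One DTI measure only: 2 × 4 × 3 | 24 | 45.5% |
| One BOLD severity score: 2 × (1 + 4×3) | 26 | 48.2% |
| No tremor maps in SD | 28 | 50.8% |
| All listed measures | 32 | 55.5% |
| BOLD mapped by three task types: 2 × 4 × (3 + 3) | 48 | 70.3% |

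Expected false maps: 28 × 0.025 = 0.7 and 32 × 0.025 = 0.8. The error passes 50% at ln 0.5 / ln 0.975 = 27.4, so at 28 independent maps.

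**Dependence.** The four voice scores come from the same recordings, and FA and MD come from the same tensor. The documents give no correlations for either, so a range was simulated: 20 patients per group, 32 maps each held at 0.025, and an FA-MD correlation of 0 or −0.7.

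| Correlation among symptoms | One test per map | 200 independent voxels per map |
|---|---|---|
| 0 | 0.53–0.56 | 0.54–0.55 |
| 0.5 | 0.48–0.50 | 0.54–0.56 |
| 0.7 | 0.43–0.45 | 0.54–0.55 |
| 0.9 | 0.33–0.34 | 0.44–0.45 |

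With no dependence and one test per map the simulation gives 0.558, against 0.555 from the formula. With 28 maps the lowest simulated value is 0.316. Dependence combined with fewer than 28 maps was not simulated and would go somewhat lower.

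**Reading B: 0.025 is the voxel threshold of the structural maps.** About 2.5% of the voxels in each structural map would then pass by chance. This affects 2 × 4 × 3 = 24 maps, or 21 without tremor in SD.

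**The case against.** The strongest defence is that the sentence is loose wording for the correction used throughout. It follows a BOLD sentence that says corrected, is introduced as similar to it, and resembles the wording of Studies 1.3.1 and 1.3.3, where the correction is over the brain. On that view 0.025 does correct for multiple comparisons, namely those over voxels, and the plan never claims control across maps. This stands as the more natural reading. It does not close the gap, because no adjustment across maps appears anywhere and the sentence gives no sign that its claim is limited to voxels.

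Four stronger readings are tempting, and the documents do not support them.

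- *A false link is more likely than not.* This needs at least 28 effectively independent maps and no true association. Several fair counts fall below 50%, as does strong dependence. Section 1.2.1 also reports earlier correlations of voice-break severity with thalamic white matter and with inferior frontal and cerebellar gray matter, so a complete absence of association is a reference case and not a forecast.
- *0.025 is 0.05/2 and so covers two tests.* The numbers match, but the plan does not give this origin.
- *The sentence replaces whole-brain correction in the structural maps.* The omission of 'corrected' leaves this open without establishing it.
- *These correlations will serve as diagnostic markers.* Section 1.4 ties diagnosis to the disorder patterns found across Aim 1. For the correlations, Study 1.3.4 claims only possible usefulness in assessing treatments.

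Naming one primary symptom per group is also a design choice in a mechanistic study. Stating openly that no adjustment is made across maps would be acceptable.

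**Conclusion.** The point holds as a gap between the claimed correction and the tests listed. On the charitable reading, the plan controls error within each map at 0.025 and not at all across maps. With no true association, family-wise error is about 51% to 56% for 28 to 32 independent maps, and roughly 33% to 70% over the other counts and dependence examined. Even the low end is about 13 times 0.025 (0.33 / 0.025 = 13.2). If the structural maps used 0.025 per voxel, the error would be much larger.

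These figures rest on an inferred map count, on each map truly being held at 0.025, and on assumed correlations among symptoms and between FA and MD. The conclusion that nothing adjusts across maps depends on none of these.

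**What to change.** 1. State that the VBM and DTI correlation maps use the same whole-brain cluster or family-wise correction as the corresponding group analyses.
2. Delete the statement that an alpha of 0.025 by itself corrects for multiple comparisons.
3. Choose one of two courses:
   - Pre-name a small confirmatory family. One example is voice breaks in SD and tremor severity in SD/VT, the two variables that Study 1.3.1 already singles out. Apply Holm across the four imaging measures at 0.025 in each group, using the smallest whole-brain-corrected p-value of each map. The first Holm step is 0.025 / 4 = 0.00625, and both groups together stay within 0.025 + 0.025 = 0.05.
   - State plainly that no adjustment is made across maps.
4. In either case, label all other maps exploratory.

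The cost is wording and fewer maps called significant; no new data are needed. A small family is far less severe than a Bonferroni correction over every map, which would require 0.025 / 32 = 0.00078 per map.
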